7.4 Eligibility criteria for reinjection

At the end-of-cycle 1 visit V8 at Week 24 (Day 168), subjects are evaluated for eligibility to continue in the bilateral treatment period (Cycle 2) of the study. Only subjects meeting all of the following criteria will be considered for reinjection in the bilateral treatment period. In this case, the Cycle 2 baseline visit V8 (Day 1) will be performed on the same day.

Subjects who do not meet these eligibility criteria will be discontinued from the study.

In case of a public health emergency, e.g. due to a COVID-19 outbreak in which the study or study visits for subjects in Cycle 1 were put on hold or in any way modified so that V8 could not be performed according to study plan (e.g. more than 25 weeks after Cycle 1 injection at baseline visit V2), subjects will not continue the study with Cycle 2 baseline visit V8 but will continue the study visit with V8a ([Section 9.2](#)). Then the eligibility criteria for study resumption of the bilateral treatment period (Cycle 2) in [Section 7.4.1](#) for V8a apply and must be utilized.

Eligibility criteria for reinjection for Visit 8	Rationale
1. Combined agreement of subject and investigator on the subject's potential benefit from study treatment of both ULs.	Efficacy, safety
2. Visible tremor of both ULs as assessed by the investigator on TETRAS Performance subscale item 4 with a score of ≥ 1.5 in either the forward horizontal reach posture, and/or lateral 'wing beating' posture and/or finger-nose(chin)-finger movement.	Efficacy
3. Body weight ≥ 50 kg.	Safety
4. Negative pregnancy test (for females of childbearing potential).	Safety
5. Absence of any infection or inflammation in the areas of the planned injection sites.	Safety
6. Absence of medically relevant, severe, or any serious AEs that are judged to have a causal relationship to the study treatment.	Safety

Eligibility criteria for reinjection for Visit 8	Rationale
7. For subjects on coumarins or other anticoagulants monitored by INR, the investigator confirms and documents that the subject has an INR value of ≤ 2.5 . Treatment with direct thrombin inhibitors, factor Xa inhibitors, heparin or heparinoids must have remained unchanged between the screening (V1) and reinjection (V8) visits.	Safety
8. No treatment with any BoNT other than study medication since baseline visit V2.	Efficacy, Safety
9. No acute COVID-19; no COVID-19 or positive SARS-CoV-2 test indicative of an acute infection in the past 14 days.	Safety
INR=International normalized ratio.	

7.4.1 **Eligibility criteria for study resumption of the bilateral treatment period (Cycle 2) in case of a public health emergency, e.g., due to a COVID-19 outbreak**

In case of a public health emergency, e.g., due to a COVID-19 outbreak in which the study or study visits for subjects in Cycle 1 were put on hold or in any way modified so that V8 could not be performed according to study plan (e.g., more than 25 weeks after Cycle 1 injection at baseline visit V2), subjects will not continue the study with Cycle 2 baseline visit V8, but will continue the study visit with V8a when possible (as outlined in [Section 9.2](#)). In this case, subjects need to fulfill the following eligibility criteria for study resumption below.

Subjects not meeting all of the eligibility criteria for study resumption due to an acute event (e.g. due to an inflammation of the planned injection site) can be re-assessed only once when the issue has been resolved.

Subjects who do not meet the eligibility criteria in the table below will be discontinued from the study.

Eligibility criteria for study resumption in case of a public health emergency	Rationale
1. Written re-consent obtained on current approved ICF version. ^a	Administrative
2. Subject does not meet any of the criteria that lead to discontinuation, as mentioned in chapter 7.5.1. This includes any	Efficacy, safety

condition which arose or treatment which was started (e.g. intrathecal baclofen) which in the opinion of the investigator no longer justifies or permits safe participation of the subject or significantly interferes with the study.	
3. At least 16 weeks passed since the last treatment with any BoNT product for any reason.	Efficacy, safety
4. No concurrent use of antibiotics that interfere with neuromuscular transmission, such as aminoglycoside antibiotics (e.g., streptomycin sulphate, kanamycin sulphate, gentamicin sulphate, neomycin sulphate, spectinomycin hydrochloride), polypeptide antibiotics (e.g. polymixin B sulphate), lincomycin antibiotics (e.g. lincomycin hydrochloride, clindamycin), or enviomycin sulphate.	Efficacy, safety
5. No treatment with parenterally administered drugs that interfere with neuromuscular transmission (e.g., intrathecal baclofen, tubocurarine-type muscle relaxants used in anaesthesia), aminoquinolines, or local anesthetics in the treated region within two weeks before the study resumption or intended to be administered during the study.	Efficacy, safety
6. Women of childbearing potential ^b must be using a highly effective method of birth control ^c and must be willing to continue using this during the entire study period.	Safety
7. Understanding of study procedures and willingness to abide by all procedures during the course of the study.	Administrative
8. No acute COVID-19; no COVID-19 or positive SARS-CoV-2 test indicative of an acute infection or symptoms suspicious of COVID-19 (e.g. fever, tiredness, dry cough) in the past 14 days.	Safety
9. Combined agreement of subject and investigator on the subject's potential benefit from study treatment of both ULs.	Efficacy, safety
10. Visible tremor of both ULs as assessed by the investigator on TETRAS Performance subscale item 4 with a score of ≥ 1.5 in either the forward horizontal reach posture, and/or lateral 'wing beating' posture and/or finger-nose(chin)-finger movement.	Efficacy
11. Body weight ≥ 50 kg.	Safety
12. Negative pregnancy test (for females of childbearing potential).	Safety

13. Absence of any infection or inflammation in the areas of the planned injection sites.	Safety
14. Absence of medically relevant, severe, or any serious AEs that are judged to have a causal relationship to the study treatment.	Safety
15. For subjects on coumarins or other anticoagulants monitored by INR, the investigator confirms and documents that the subject has an INR value of ≤ 2.5 . For subjects on direct thrombin inhibitors, factor Xa inhibitors, heparin or heparinoids, the investigator confirms and documents that the therapy has remained unchanged since screening (V1) or that the subject has an aPTT time ≤ 80 seconds.	Safety

INR=International normalized ratio.
 
a. Written re-consent is necessary if new ICF version is available or if more than 2 months have passed between the end-of-cycle visit and the re-start assessment.
 
b. Childbearing potential is defined as neither premenarche, nor permanently sterilized nor postmenopausal (i.e. 12 months with no menses without an alternative medical cause).
 
c. Defined as a method that results in a low failure rate (i.e. less than 1% per year) when used consistently and correctly, such as implants, injectables, combined oral contraceptives, some intrauterine devices, sexual abstinence, or vasectomized partner.
	

7.5 Removal of subjects from treatment or assessment

7.5.1 Discontinuation of subject's study participation

In accordance with the Declaration of Helsinki and the ICF, the subject may end his/her participation in the study at any time without any penalty or loss of benefits to which the subject is otherwise entitled, see [Section 7.5.3](#). Both the fact and the reason(s) why the subject's participation in the study was prematurely discontinued must be recorded in the source documentation (e.g. subject file) and the eCRF. Date and discontinuation circumstances should be stated.

The investigator **must** discontinue the subject's study participation at any time, if any of the following occurs:

- Withdrawal of informed consent.
- Treatment with any other IP in another clinical study.
- Treatment with any BoNT other than IP, except in case of a public health emergency, as specified below.

- In case the study was on hold or the study was not performed according to plan for a subject in case of a public health emergency, e.g. due to a COVID-19 outbreak, the treatment with any BoNT other than study medication to ensure subject's well-being does not lead to discontinuation (please refer also to [Section 7.4.1](#)). Injections of BoNT of any serotype (other than the IP) are permitted only if the subjects have completed their end-of-cycle 1 visit V8 (by phone). In this case subjects cannot resume the study until at least 16 weeks have passed since their last injection with any other BoNT than the study medication and this time-period must be considered for performance of V8a. Pregnancy (no further administration of IP(s), blood sampling, or any other interventional procedure will be performed).
- Any AE for which treatment continuation would constitute an unacceptably high risk for the subject.
- Any other condition arises which in the opinion of the investigator no longer justifies or permits safe participation of the subject or which significantly interferes with the study assessments so that participation is no longer justified.
- Any eligibility criterion not met for reinjection or resumption.

Deviations from this study protocol, or conditions comprising exclusion criteria established in [Section 7.3](#) that arise after the subject has been included in the study may (but will not necessarily) lead to the discontinuation of subject's study participation. All such conditions must be properly documented. Any deviations related to a public health emergency, e.g., due to a COVID-19 outbreak (e.g., visit deviations, remote assessments, rater change due to staff being unavailable in case of a public health emergency) must be documented as such. Subjects who discontinue the study because of AEs will be treated according to standard clinical procedures. For any subject discontinuing the study, the end-of-study visit (V11) should be conducted. All pertinent information concerning the AE will be documented in the source documentation as well as in the eCRF report form until V11. No information will be collected in the eCRF thereafter.

The investigator is required to make every effort to contact subjects lost to follow-up, and all such efforts are to be documented in the source documentation (e.g. times and dates of telephone contact, copies of letters).

Subjects who discontinue the study will not be replaced.

7.5.2 Premature termination or suspension of the study or closure/suspension of a study site

The study or a study site can be prematurely terminated or suspended by the sponsor. Reasons for termination of the study or closure of a study site may include, but are not limited to, the following:

- Subject enrollment is unsatisfactory;
- The risks and benefits of continuing the study have been reassessed, and the risks outweigh any potential benefits;
- The incidence of AEs constitutes a potential health hazard to the subjects;
- New scientific data on the IP(s) do not justify a continuation of the study;
- The investigator or study site exhibits serious and/or persistent non-adherence to the clinical study protocol, the Declaration of Helsinki, ICH-GCP, and/or applicable regulatory requirements; and
- The sponsor decides to terminate or suspend the study at any time for any other reason. The study may be prematurely ended if the regulatory authority or the IEC/IRB has decided to withdraw or suspend approval for the study, the study site, or the investigator.

If the study is prematurely terminated or suspended for any reason, the investigator must inform the subjects and ensure appropriate follow-up treatment. Within the timeframes noted in applicable regulations, the sponsor will promptly inform the investigators, the IEC/IRB, and regulatory authorities of the termination or suspension of the study, as well as provide reasons for the action.

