The duration of observation following administration of NT 201 was chosen on the basis of the predecessor study [Jog 2017, Merz Pharmaceuticals GmbH 2017], in which wrist tremor amplitude reduction was observed until 24 weeks after injection with NT 201. The current study also aims to follow up subjects in the unilateral treatment period for 24 weeks. That period is deemed sufficiently long to allow for reinjection and to investigate individual differences in duration of response. An observation period of 12 weeks after reinjection (the typical injection interval with NT 201 in approved therapeutic indications) is considered sufficient for follow-up of safety and efficacy well beyond peak effects. No further reinjection is planned after completion of the study.

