8.2.4 Duration of treatment per subject

Overall, the duration of the study will be 36 weeks plus up to 3 weeks screening period.

Each subject will receive injection of NT 201 or matching placebo into the motor dominant UL on Day 1 of the unilateral treatment period (Cycle 1), followed by a 24-week observation period, and injection of NT 201 into both arms on Day 1 of the bilateral treatment period (Cycle 2), followed by a 12-week observation period.

In case of public health emergency measures, e.g., due to a COVID-19 outbreak the treatment may be halted or postponed (see [Section 6.1](#) and [7.5.4](#)). If a subject is affected by the treatment halt due to a COVID-19 outbreak, the study duration will be extended by the duration of the hold (see [Section 7.4.1](#)).

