10.3 Adverse events of special interest (alert terms)

AESIs are considered to have a special meaning or importance for a particular drug or class of drugs. They may be non-serious and precursors (prodromes) of more serious medical conditions. Therefore, they should be closely monitored and promptly reported to the CRO. Subjects will be actively asked at each visit (beginning at V2) by the investigator or his/her authorized delegate if any AESI terms occurred since the last contact. The questioning and documentation will be standardized. For confirmation of certain AESI terms, the investigator may require a physical and/or neurological examination to assess the event.

AESIs for this study are listed in [Table 7](#).

The site must report all AESIs that occur during the study period, whether considered to be related to IP or not, by telefax, or email to the responsible CRO within 24 hours of knowledge of the event. The CRO will transmit these AESIs to the sponsor. Each AESI must be reported by the site on the AESI reporting form. Moreover, AESIs should be documented on the general pages of the AE eCRF as well as in the subject file.

The AE form in the eCRF as well as the eCRF forms for medical history/concomitant diseases and for previous/concomitant medication and non-drug treatment are to be faxed/sent along with the AESI reporting form. For contact details, see [Section 2.2](#).

Serious AESIs will be followed up until recovered/resolved or a plausible explanation is available. Non-serious AESIs will not be followed up after the subject's end-of-study visit.

Table 7: List of adverse events of special interest

MedDRA Preferred Term (MedDRA version 23.0)		
Accommodation disorder	Eyelid function disorder	Peripheral nerve palsy
Areflexia	Eyelid ptosis	Peripheral paralysis
Aspiration	Facial paralysis	Pelvic floor muscle weakness
Botulism	Facial paresis	Pneumonia aspiration
Bradycardia	Hemiparesis	Pupillary reflex impaired
Bulbar palsy	Hypoglossal nerve paresis	Quadriparesis
Constipation	Hyporeflexia	Respiratory arrest
Cranial nerve palsies, multiple	Hypotonia	Respiratory depression
Cranial nerve paralysis	IIIrd nerve paresis	Respiratory failure
Diaphragmatic paralysis	Ileus paralytic	Speech disorder
Diplopia	IVth nerve paresis	Trigeminal nerve paresis
Dry mouth	Monoparesis	Urinary retention
Dysarthria	Muscular weakness	Vision blurred
Dysphagia	Paralysis	Vocal cord paralysis
Dysphonia	Paraparesis	Vocal cord paresis
Dyspnoea	Paresis	

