10.6 Pregnancy

Each pregnancy that starts during the study must be reported by the investigator to the product safety department of the CRO within 24 hours of learning of its occurrence. Pregnancies and pregnancy follow-up should be reported on a pregnancy monitoring form. Pregnancy follow-up should describe the outcome of the pregnancy, including any voluntary or spontaneous discontinuation; details of the birth; the presence or absence of any congenital abnormalities, birth defects, maternal or newborn complications, and their relation to the IP(s). Each normal pregnancy is to be reported as a non-serious AE (drug exposure before or during pregnancy). Any abnormal pregnancy or pregnancy outcome is to be reported as SAE (on an SAE form).

In case of pregnancy prior to injection, the subject must not receive any IP and the end-of-study visit will be conducted right away without any invasive procedures (such as blood drawing) performed.

If a pregnancy occurs after a subject has received injection, the subject must not receive any further IP and the end-of-study visit (V11) will be conducted right away without any invasive procedures (such as blood drawing) performed.

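### An adverse event that makes reinjection too risky ends study participation, so follow-up of non-serious events stops at the exit visit although the current cycle's injection cannot be withdrawn

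*Protocol*

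**What the plan says.** Protocol 7.5.1 obliges the investigator to "discontinue the subject's study participation at any time, if any of the following occurs", and one listed trigger is "Any AE for which treatment continuation would constitute an unacceptably high risk for the subject". The end-of-study visit (V11) is then held and AE documentation runs up to it: "No information will be collected in the eCRF thereafter".

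Protocol 8.2.4 describes two treatment sessions. In the first, "Each subject will receive injection of NT 201 or matching placebo into the motor dominant UL on Day 1 of the unilateral treatment period", with 24 weeks of observation. The second is "injection of NT 201 into both arms on Day 1 of the bilateral treatment period (Cycle 2), followed by a 12-week observation period". Protocol 8.2.3 permits no others. Separately, criterion 6 of Protocol 7.4 bars reinjection at V8 after medically relevant, severe or serious AEs judged related.

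After exit, Protocol 10.3 says "Non-serious AESIs will not be followed up after the" end-of-study visit, and Protocol 10.1 says the same of non-serious AEs. SAEs (10.2) and serious AESIs (10.3) are followed until resolved or explained. SAP 4.6.1 generally expects no visits after premature discontinuation.

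**The concern.** A judgement about whether further treatment is safe is used to end observation. For a drug given daily, stopping treatment at least removes exposure. Here the injection of the current cycle is already in the muscle, so leaving the study removes no exposure until the next session, and that session has its own AE gate.

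The subjects affected are chosen because they had an adverse event. Safety of NT 201 against placebo is a secondary objective, and muscular weakness is a listed AESI term that can be severe in intensity without being serious. If such events are more frequent on NT 201, the loss falls unevenly on the two arms. The result would be understated duration and incomplete outcome for the non-serious events of most interest.

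**Working it through.** **1. The plan's own figure.** Protocol 12.1 gives 51 analyzable subjects for an effect of 1 SD, two-sided 5%, 2:1 allocation and 90% power. A two-sample t-test (noncentral t) needs 16.43 placebo subjects, rounded up to 17, so 17 + 34 = 51 with power 0.910. The figure is reproduced. With 25 placebo and 50 NT 201 subjects, power at 1 SD is 0.981. Losing 1 to 5 NT 201 subjects leaves 0.980 to 0.977. Power is not the issue.

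**2. What the trigger can act on.**

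| When the AE occurs | Treatment still to come | Other rule barring it | Effect of exit on current exposure |
|---|---|---|---|
| Cycle 1, after the Day 1 injection | Bilateral reinjection at Week 24 | Protocol 7.4, criterion 6 (related AEs) | None |
| Cycle 2, after the Day 1 injection | None | Not needed | None |

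**3. Planned observation lost per subject.** Loss = 24 − exit week (Cycle 1) or 12 − exit week (Cycle 2). The exit weeks are assumptions; the documents give none.

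| Exit week | Cycle 1 weeks lost (of 24) | Cycle 2 weeks lost (of 12) |
|---|---|---|
| 4 | 20 (83%) | 8 (67%) |
| 6 | 18 (75%) | 6 (50%) |
| 12 | 12 (50%) | cycle complete |

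SAP 4.1.2.1 reports both key secondary endpoints complete for all treated subjects. An exit before the Week 6 assessment therefore did not occur here, and the Week 4 row for Cycle 1 is a planning case only. SAP 4.7.4 maps an exit visit from Day 36 onward to Week 6, so the largest Cycle 1 loss in this trial is about 18 to 19 weeks ((168 − 36)/7 = 18.9).

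**4. How many subjects.** Protocol 4.3 reports, for the predecessor study, muscular weakness in two NT 201 subjects (10.5%, so about 19 treated), all reactions mild, and no AE leading to discontinuation. The rate relevant to an exit rule is 0/19. Its exact 95% upper limit is 1 − 0.025^(1/19) = 17.6%. For 50 NT 201 subjects that is a point estimate of 0 and an upper limit of 50 × 0.176 = 8.8, about 9.

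**5. Person-time.** Planned NT 201 Cycle 1 time is 50 × 24 = 1,200 person-weeks. For exits at Week 6:
- 1 to 5 subjects: 18 to 90 person-weeks (1.5% to 7.5%).
- 9 subjects: 9 × 18 = 162 person-weeks (13.5%).

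The share is modest; what matters is that it comes entirely from subjects selected by an AE.

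**6. What the analysis does with an exit.**
- SAP 4.5 keeps the subject in the TEAE denominator and states no exposure adjustment, so later events go uncounted.
- SAP 4.5 does not impute AE end dates and sets duration to missing without a stop date, so events open at exit contribute no duration.
- SAP 4.7.4 remaps exit-visit data to the nearest scheduled visit only for TETRAS and kinematic assessments. Grip strength measured at a Cycle 1 exit is not placed at a Cycle 1 visit.

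**The case against.** The strongest reply is that serious reactions are already protected. Persistent or significant disability and medically important conditions count as SAEs (Protocol 10.2) and are followed until resolved or explained. Protocol 9.2 allows telephone or clinic contact for SAEs ongoing at V11, and related SAEs stay reportable after the observation period. A full exit visit is held, with grip strength, laboratory tests and AESI questioning. The trigger is also narrow: it concerns reinjection months ahead of a slowly reversible toxin, so nothing compels exit for weakness that may resolve. All of this stands. It confines the point to non-serious events, scheduled assessments and what reaches the study database; after reconciliation, SAE follow-up sits only in the sponsor's safety database.

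Several stronger inferences are tempting, and the documents do not support them:
- *No treatment remains once a subject is injected.* A second, bilateral session is planned; the statement holds only within a cycle or after the Cycle 2 injection.
- *About 5 of 50 NT 201 subjects would be lost.* That applies 10.5% to 50, but those were mild weakness cases and none left the study.
- *Ineligibility at V8 truncates follow-up.* Such a subject has completed the 24 Cycle 1 weeks; only the outcome of a non-serious event still open is lost.
- *Pregnancy has the same consequence.* Under Protocol 10.6 "the subject must not receive any further IP and the end-of-study visit (V11) will be conducted right away", but pregnancy outcome is then followed on its own form.
- *The 24 weeks are a safety requirement.* Protocol 6.2 cites that "wrist tremor amplitude reduction was observed until 24 weeks after injection with NT 201", together with reinjection timing and duration of response. It regards 12 weeks after reinjection as enough for safety follow-up.

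**Conclusion.** The point holds in a limited form. The AE bullet in Protocol 7.5.1 links a judgement on further treatment to compulsory exit. That reduces no exposure in the current cycle and stops eCRF data, scheduled visits and non-serious AE and AESI follow-up at the exit visit. The loss is selected by AE and could be uneven between arms, on the assumption that such events are commoner on NT 201.

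The size per affected subject can be large, at 18 of 24 weeks for an exit at Week 6. The number affected is unknown and may be zero: the predecessor study suggests 0 of 50, with an upper limit of about 9. A reader might infer that the primary analysis is biased by AE-driven dropout before Week 6. The completeness of both key secondary endpoints gives no support for that here, although the SAP makes no equivalent statement about the primary endpoint. This is a cheap improvement in safety data, not a threat to the primary conclusion.

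**What to change.** Reconcile Protocol 7.4, 7.5.1, 10.1 and 10.3 so that barring further investigational product and ending study participation are separate outcomes. For the AE bullet, keep consenting subjects in the visits already scheduled to the end of the current cycle (V8 or V11), on site or by the remote route in 9.1.1.1. That route is now limited to public health emergencies and would need to be opened for this use; it collects AEs and AESIs but not grip strength. No criterion for withholding treatment changes. SAP 4.6.1 and 4.7.4 would each need a line so that these visits are expected and analyzed at their scheduled time.

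The blinded data review took place on 17 January 2024, so for this trial the practical step may be reporting only. By arm, tabulate AE-driven exits, their follow-up time and AESIs unresolved at exit. The SAP already summarizes cycle length and lists TEAEs leading to discontinuation, so this is one added table. The wording change then serves any remaining conduct and later protocols.

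The cost is an amendment to wording; the visits are already in the schedule. The downside is that some subjects may decline further visits.
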